7.4 Evaluation at Completion of Study Intervention

Seven to fourteen days after the last scheduled vaccine dose, participants will return for the post-intervention visit. Blood will be collected for CBC-diff, CMP, PSA, PBMCs, and serum prior to the digital rectal exam and collection of the post-intervention biopsy. Participants will be evaluated for weight, vital signs, AEs and concomitant medications. International Prostate Symptom Score will be obtained. DRE will be performed at the discretion of the individual urologist. TRUS-guided prostate biopsy or targeted prostate biopsy using MR-US fusion will be performed as part of the routine care of patients on active surveillance.

Pre- and post-intervention biopsy pathology reports will be collected, de-identified, labeled with study ID and participant ID and submitted to the University of Arizona Early Phase Chemoprevention Consortium Office.

Report Submission Information:
University of Arizona Early Phase Chemoprevention Consortium Office
Attn: [name]
[name]
[name]
[contact]
[contact]
Email: [contact]

Unstained tissue slides from the pre- and post-intervention prostate biopsies will be requested from the institutional pathology lab for analysis of the immunologic response in the target tissue.

If available, reports from the prostate MRI scans (and companion pathology reports) performed from 3 years prior to and 6 months after the study intervention will be collected. Reports will be de-identified, labeled with study ID and participant ID and submitted to the University of Arizona Early Phase Chemoprevention Consortium Office to capture the lesion size information.

The results of all PSA tests performed throughout the intervention as part of the routine care of patients on active surveillance will be collected.

7.5 Post-intervention Follow-up Period

Study subjects will be followed for 30 days after the last study dose is given. Participants will continue to record adverse events during the 30-day follow-up period. The diary will be mailed back to the study staff in a pre-addressed, stamped envelope. Study staff will contact the subject by phone to clarify any of the diary entries, if necessary.

Participants will return for a follow-up visit 6 months (5-7 months) after the post-intervention biopsy or 6 (5-7 months) months after the last study dose is given, if no post-intervention biopsy was performed, as part of the standard-of-care. Blood will be collected for PSA. Participants will be interviewed for interval medical history including autoimmune disease. International Prostate Symptom Score will be assessed and active surveillance status will be documented. DRE will be performed at the discretion of the individual urologist. Patients who have undergone prostatectomy, radiation therapy or focal prostate cancer therapy are exempt from the six-month follow-up visit requirement.

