5.2 PROSTVAC® Administration

- Participants will receive subcutaneous injection of PROSTVAC® or placebo in the study clinic injected into the upper outer thigh or upper arm. It is recommended to alternate the injection sites.
- The treatment regimen will include a priming vaccination with subcutaneous injection of 2×10^8 pfu (in 0.5 mL) of PROSTVAC-V or placebo (empty vector) at baseline, followed by booster vaccinations with subcutaneous injection of 1×10^9 pfu (in 0.5 mL) of PROSTVAC-F or placebo (empty vector) on Day 14, 28, 56, 84, 112, and 140 following the priming injection.
- Participants should remain in the clinic for at least 30 minutes following administration of PROSTVAC-V/F or placebo for observation for signs of adverse reactions.

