⁹At the Day 84 visit, CBC-diff and CMP will need to be evaluated to determine whether the injection on that day may be given or omitted and whether there is the need to repeat the safety labs before the next scheduled injection. If needed, the labs can be done on a different day prior to the day for the vaccine injection, but the labs and the vaccine injection should fall within the window specified on the schedule of events.

¹⁰Subjects to be followed for 30 days after the last study dose is given. Participants will be asked to keep a 30-day diary and mail it back to the study staff in a pre-addressed, stamped envelope.

¹¹6 months (5-7 months) following the post-intervention biopsy or 6 months (5-7 months) after the last study dose is given, if no post-intervention biopsy was performed, to be performed as part of the standard-of-care.

¹²If available, reports from the prostate MRI scans (and companion pathology reports) performed from 3 years prior to and 6 months after the study intervention will be collected and submitted to the University of Arizona to capture the lesion size information.

¹³Patients who have undergone prostatectomy, radiation therapy or focal prostate cancer therapy are exempt from the six-month follow-up visit requirement.

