8.2 Secondary Endpoints

- 8.2.1 To assess the effect of PROSTVAC® on the change in PD-L1 positive cells in the stroma adjacent to tumor and within the malignant portion of the prostate biopsies. The change will be compared between participants treated with PROSTVAC® and those treated with placebo. A subgroup analysis will be performed to compare the change in PD-L1 positive cells between study groups in specimens collected by targeted biopsy.
- 8.2.2 To assess the correlation between the change in CD8⁺ and the change in PSA. The correlation between the change in CD8⁺ in the stroma adjacent to tumor and within the malignant portion of the prostate biopsies and the change in PSA (from baseline to 6 months (5-7 months) post-intervention) in participants treated with PROSTVAC® will be examined.
- 8.2.3 To assess the effect of PROSTVAC® on the change in CD8⁺, CD4⁺, and PD-L1 positive cells in the benign portion of the prostate biopsies. The change will be compared between participants treated with PROSTVAC® and those treated with placebo.
- 8.2.4 To assess the effect of PROSTVAC® on the change in PSA. The change in PSA from baseline to 6 months (5-7 months) post-intervention will be compared between participants treated with PROSTVAC® and those treated with placebo.
- 8.2.5 To assess the effect of PROSTVAC® on tumor grade progression, defined as a post-intervention

- Gleason score of $\geq 4+3$ using all biopsy data, i.e., from random and target biopsy cores. Proportion of men with post-intervention Gleason score of $\geq 4+3$ will be compared between the treatment groups. In addition, this endpoint will be evaluated in the subgroup of patients in whom MRI-targeted biopsies were obtained pre- and post-intervention.
- 8.2.6 To assess the effect of PROSTVAC on tumor extent based on the percent of positive random biopsy cores. The change in tumor extent will be compared between the treatment groups.
 - 8.2.7 To assess the proportion of men with no cancer in the post-intervention biopsy between participants treated with PROSTVAC® and those treated with placebo. This analysis will utilize all biopsy data, i.e., from random and target biopsy cores.
 - 8.2.8 To assess the effect of PROSTVAC on the size of the dominant lesion on MRI (largest histopathologically confirmed lesion) in the subgroup of patients with MRIs pre and post-intervention.

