 - 8.2.9 To determine the safety and feasibility of PROSTVAC® in patients with clinically localized prostate cancer undergoing active surveillance.
 - 8.2.10 To assess the change in circulating 15-Mer PSA-specific T cells.
 - 8.2.11 To assess the change in soluble antibodies to tumor-associated antigens.
 - 8.2.12 To assess the immunologic effects of PROSTVAC® on the target organ using multiplex immunofluorescence.
 - 8.2.13 To assess the effects of PROSTVAC on LUTS by evaluating changes in International Prostate Symptom Score from baseline to 6 months (5-7 months) post-intervention.

If feasible, change in tumor grade and extent will be assessed by central pathology review.

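### When no biopsy is done, the PSA and IPSS endpoint visit is timed from the last dose given, so early stoppers without a biopsy are measured about 1 to 5 months sooner after baseline than men with one (minor)

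*Combined protocol and SAP*

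**What the plan says.** Section 7.5 gives the follow-up visit two anchors. The first is the biopsy: "Participants will return for a follow-up visit 6 months (5-7 months) after the post-intervention biopsy". The second applies when there is none: the visit then falls 6 (5-7) "months after the last study dose is given, if no post-intervention biopsy was performed". Section 7.1, footnote 11, words it as "6 months (5-7 months) after the last study dose is given, if no post-intervention biopsy was performed". Section 3 states the same rule.

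PSA and IPSS are both collected at that visit. Section 8.2.4 defines the PSA endpoint: "The change in PSA from baseline to 6 months (5-7 months) post-intervention will be compared". Section 8.2.13 defines the symptom endpoint through "changes in International Prostate Symptom Score from baseline to 6 months (5-7 months) post-intervention".

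Boosters are given "on Day 14, 28, 56, 84, 112, and 140 following the priming injection" (section 5.2). For the visit at which the biopsy is taken, section 7.4 says: "Seven to fourteen days after the last scheduled vaccine dose, participants will return for the post-intervention visit". The column header in the section 7.1 table gives the same 7 to 14 days but omits the word scheduled.

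Men who stop the agent stay in endpoint follow-up where possible and appropriate (section 8.3) and in the intent-to-treat analysis (sections 13.1 and 13.6). Section 13.5 compares the continuous secondary endpoints by a two-sided two-sample t test at 5% and calls these analyses exploratory. It contains no term or rule for time since baseline.

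**The concern.** A change from baseline is comparable between men only if it covers a similar span of time. Here the span for a man without a biopsy shortens with each dose he does not receive at the end of the course, yet his value enters the same comparison as a completer's value. Multiple imputation does not address this, because his value is observed.

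Stopping and having a biopsy are both post-randomization events, and section 5.6 ends or omits injections for some adverse events. If early stopping without a biopsy were more common in one arm, that arm would have shorter average follow-up. With a slowly rising PSA, its rise would then look smaller for a reason unrelated to efficacy.

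**Working it through.** The plan states no time from baseline, sample size or power for the PSA or IPSS endpoint, so there is no figure of its own to reproduce. The check is calendar arithmetic on the plan's schedule.

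**Inputs.** Doses on Days 0, 14, 28, 56, 84, 112 and 140 (section 5.2). Biopsy 7 to 14 days after the last scheduled dose, nominally Day 147 to 154 (section 7.4). Visit 6 months later, window 5 to 7 (section 7.5). Dosing windows of ±5 days at Day 14 and ±7 days afterwards (section 7.1). One month = 30.4375 days.

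**Formula.** Months from Day 0 = anchor day / 30.4375 + 6, with 5 and 7 in place of 6 for the limits.

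| Case | Anchor day | Nominal visit day | Months from Day 0 (5-7 month window) |
|---|---|---|---|
| No biopsy, last dose Day 0 | 0 | 183 | 6.0 (5.0-7.0) |
| No biopsy, last dose Day 14 | 14 | 197 | 6.5 (5.5-7.5) |
| No biopsy, last dose Day 28 | 28 | 211 | 6.9 (5.9-7.9) |
| No biopsy, last dose Day 56 | 56 | 239 | 7.8 (6.8-8.8) |
| No biopsy, last dose Day 84 | 84 | 267 | 8.8 (7.8-9.8) |
| No biopsy, last dose Day 112 | 112 | 295 | 9.7 (8.7-10.7) |
| No biopsy, last dose Day 140 | 140 | 323 | 10.6 (9.6-11.6) |
| Biopsy Day 147 | 147 | 330 | 10.8 (9.8-11.8) |
| Biopsy Day 154 | 154 | 337 | 11.1 (10.1-12.1) |

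The largest nominal gap is 147/30.4375 = 4.8 to 154/30.4375 = 5.1 months.

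**Overlap once dosing windows are included.** The earliest completer with a biopsy has his last dose on Day 133, biopsy on Day 140 and visit 5 months later: 140 + 152 = Day 292.
- Last dose Day 56, given on Day 63, visit 7 months later: 63 + 213 = Day 276. No overlap.
- Last dose Day 84, given on Day 91: 91 + 213 = Day 304. Overlap.

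The windows are therefore disjoint only for last doses at or before Day 56.

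**Is time from last dose fixed instead?** Take two men whose last dose is on Day 28. Without a biopsy, the visit is at Day 211, which is 6 months after that dose. With a biopsy timed as in section 7.4, it is at Day 330 to 337, or (330 − 28)/30.4375 = 9.9 to (337 − 28)/30.4375 = 10.2 months after the same dose. The rule fixes neither interval.

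**Size, on assumed PSA kinetics.** The documents give no PSA trajectory. Assume a baseline of 6 ng/mL and a doubling time (DT) of 3 to 10 years. Rise = 6 × (2^(t/DT) − 1).
- DT 120 months: 0.21 at 6 months, 0.39 at 11 months, difference 0.18.
- DT 36 months: 0.73 at 6 months, 1.42 at 11 months, difference 0.68 (from unrounded values).

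Projected attrition is 10% of 150 = 15 men (section 13.4).
- 10% of one arm affected at the extreme, none of the other: 0.10 × 0.18 to 0.68 = 0.02 to 0.07 ng/mL in the arm mean.
- All 15 in the PROSTVAC arm, all prime-only, none biopsied, all attending: 15/100 × 0.18 to 0.68 = 0.03 to 0.10 ng/mL.

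**The case against.** The strongest defence is that post-intervention means a fixed time off treatment, so a visit 6 months after the last dose is what was intended. The comparison of two men stopping on Day 28 answers this: on section 7.4's text, identical exposure leads to visits about 4 months apart, depending only on whether a biopsy was done.

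Other parts of the defence stand:

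- Many early stoppers should not be affected. Section 5.6 says men taken off the agent for a related Grade 4 event should, if appropriate, remain on study and have the biopsy, and section 8.3 keeps men off agent in endpoint collection. On section 7.4's text they are seen at about 11 months. For related Grade 2 or 3 events an injection is omitted and dosing can resume, so the last-dose date moves only if the final doses are the ones missed.
- The 10% attrition also covers withdrawals and completers who decline biopsy. Completers without a biopsy are seen at 10.6 months, which is no problem.
- The explanatory analysis in section 13.6 requires two or more boosts, which removes the men nearest 6 months.
- Only secondary endpoints, declared exploratory, are involved.

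A reader might also infer that the rule adds noise to the CD8-PSA correlation in section 8.2.2. The documents do not support that to any material degree: the last-dose anchor applies only to men without a post-intervention biopsy, and they have no observed post-intervention CD8 value. They could enter that analysis only through imputation.

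**Conclusion.** The point holds as a minor one, worth considering because the remedy is cheap. The rule gives early stoppers without a biopsy a nominal 6.0 to 9.7 months from baseline, against 10.8 to 11.1 months for men with a biopsy, and the planned analysis takes no account of the difference. The timing figures follow from the plan's schedule. The PSA figures rest on the assumed baseline and doubling times. The 0.1 ng/mL figure is the top of that range with every projected drop-out placed at the extreme in the PROSTVAC arm, so the likely shift is smaller.

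Three stronger readings are not supported:

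- That early stoppers in general are measured at 6 months. That fits only men who stop after the prime or first boost and have no biopsy.
- That the visit windows are disjoint for last doses up to Day 84. This fails once the ±7-day dosing windows are applied.
- That the arm comparison is biased. Bias requires early stopping without a biopsy to differ between arms, and the documents give no figure for that.

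**What to change.** 1. In section 3, section 7.5 and section 7.1 footnote 11, for men without a post-intervention biopsy, time the follow-up visit from the date of the last scheduled dose (Day 140 from the Baseline Visit) instead of the last dose given. The nominal visit is then Day 323 (10.6 months) whatever the stopping day, against Day 330 to 337 with a biopsy. The nominal spread falls from about 5 months to 11.1 − 10.6 = 0.5 month, apart from the 5-7 month window.
2. Reconcile the section 7.1 column header with section 7.4 on whether the post-intervention visit is counted from the last dose or the last scheduled dose. If the header were read as the last dose given, a prime-only stopper with a biopsy would be seen at 7/30.4375 + 6 = 6.2 to 14/30.4375 + 6 = 6.5 months, and item 1 would not reach him.
3. Report actual days from baseline to the endpoint PSA and IPSS by arm.

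The cost is a wording change in three places, one reconciliation and one descriptive table, with no added procedure. The downside is that a few early stoppers are assessed later than now planned, with slightly more risk of loss to follow-up.

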4.2 Exclusion Criteria

- 4.2.1 Have had prior treatment for prostate cancer by surgery, irradiation, local ablative (i.e., cryosurgery or high-intensity focused ultrasound), or androgen-deprivation therapy.
- 4.2.2 Patients who have prostate cancer with distant metastases.
- 4.2.3 Have undergone treatment of hormone therapy, immunotherapy, chemotherapy and/or radiation for any malignancies within the past 2 years.
- 4.2.4 Uncontrolled intermittent illnesses or medical conditions which, in the opinion of the treating physician, would make this protocol unreasonably hazardous for the patient. Such illnesses/conditions may include, but are not limited to, ongoing or active infection, symptomatic congestive heart failure, unstable angina pectoris, symptomatic or unstable cardiac arrhythmia, or psychiatric illness/social situations that would limit compliance with study requirements.
- 4.2.5 Positive for HIV or active infections for hepatitis B, and /or hepatitis C, based on medical history.
- 4.2.6 Prior solid organ or bone marrow transplant.
- 4.2.7 Immunodeficiency or splenectomy.
- 4.2.8 Chronic immunosuppressive therapy within 30 days of screening.
- 4.2.9 Inflammatory eye disease requiring steroid treatment within 28 days of screening.
- 4.2.10 Chronic administration (defined as daily or every other day for continued use > 14 days) of systemic corticosteroids within 28 days of the first planned dose of PROSTVAC-V/F. Use of inhaled steroids, nasal sprays, and topical creams for small body areas is allowed.
- 4.2.11 History of or active autoimmune disease including but not limited to autoimmune neutropenia, thrombocytopenia, or hemolytic anemia, systemic lupus erythematosus, Sjogren's syndrome, scleroderma, myasthenia gravis, Goodpasture's syndrome. Persons with vitiligo are not excluded. Persons with well-controlled autoimmune endocrinopathies, e.g., diabetes mellitus, Graves' disease, Hashimoto's thyroiditis, Addison's disease are not excluded. Persons with well-controlled rheumatoid arthritis, psoriatic arthritis and polymyalgia rheumatica are not excluded.
- 4.2.12 Known allergy to eggs, egg products.
- 4.2.13 Prior or concurrent eczema or other eczematoid skin disorders or active skin condition (acute, chronic, or exfoliative) that disrupts the epidermis. Persons with psoriasis are not excluded except in cases of:
 - any active lesion
 - any active lesion in the previous 6 months that required treatment, either systemic or topical

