On 14, 28, 56, 84, 112, 140 days following the Baseline Visit, participants will return for interim study visits. Participants will receive booster vaccinations with subcutaneous injection of PROSTVAC-F or placebo, injected into the upper outer thigh or upper arm. It is recommended to alternate the injection sites. Prior to the first booster injection, participants will be evaluated for evidence of bacterial infection, blisters, vesicles or evidence of persistent infection. Weight, vital signs, AEs and conmed information will be collected at each interim visit. At the Day 84 visit, International Prostate Symptom Score will be obtained and blood will be drawn for PSA, CBC-diff, and CMP prior to administration of the vaccine injection. CBC-diff and CMP will need to be evaluated to determine whether the injection on that day may be given or omitted and whether there is the need to repeat safety labs before the next scheduled injection. If needed, the labs can be done on a different day prior to the day for the vaccine injection, but the labs and the vaccine injection should fall within the window specified on the schedule of events. The Day 14 visit can be scheduled +/- 5 days. The Day 28, 56, 84, 112, 140 interim visits can be scheduled +/- 7 days. The vaccine injection may be omitted due to adverse events (as described in section 5.6).

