8.4 Off-Study Criteria

Participants may go ‘off-study’ for the following reasons: the protocol intervention and any protocol-required follow-up period is completed, adverse event/serious adverse event, lost to follow-up, non-compliance, concomitant medication, medical contraindication, withdraw consent, death, and determination of ineligibility (including screen failure). Study subjects will be followed for 30 days after the last study dose is given.

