For both primary and secondary endpoints, data will be tested for non-normality and outliers. If the normality assumption is violated, a potential transformation will be sought. If no suitable transformations can be found, nonparametric tests (e.g. Wilcoxon Rank Sum test and Spearman correlation coefficient) will be used. If outliers are detected, sensitivity analysis will be performed to evaluate the impact of the outliers on the effects of PROSTVAC®. In addition, we anticipate observing a missing rate of 25% or greater for both primary and secondary endpoints. The missing rates for both PROSTVAC® and placebo groups will be reported and compared. Also, regression models will be performed to identify the potential variables that are predictive of the missing endpoints or probabilities.

Descriptive statistics of the type and frequency of all adverse events will be generated, including 95% confidence intervals. For each type of the adverse events, a Fisher's exact test will be performed to compare the frequency of the adverse event between the two groups.

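### The 6-month autoimmune question has no defined route into the safety result, and men who had definitive therapy are not asked it at that visit

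*Combined protocol and SAP*

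**What the plan says.** **Where the plan asks about autoimmune disease.** Exclusion 4.2.11 covers "History of or active autoimmune disease including but not limited to autoimmune neutropenia, thrombocytopenia, or hemolytic anemia", among other conditions. Well-controlled endocrinopathies, rheumatoid and psoriatic arthritis and polymyalgia rheumatica may enter. Schedule footnote 1 puts autoimmune disease into the medical history, and at 6 months 7.5 states "Participants will be interviewed for interval medical history including autoimmune disease".

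**When AE collection appears to stop.** Section 8.4 states "Study subjects will be followed for 30 days after the last study dose is given"; footnote 10 and 7.5 give the same period. Section 7.5 adds "Participants will continue to record adverse events during the 30-day follow-up period". In the schedule (7.1), the Adverse Events row is marked at baseline, at each dosing visit and at safety follow-up, and is blank at 6 months.

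**Where no end is stated.** Section 11.1.1 requires all AEs after consent and baseline assessments to be recorded. Section 13.7 makes participants evaluable for toxicity from the first dose. Section 13.5 promises "Descriptive statistics of the type and frequency of all adverse events will be generated, including 95% confidence intervals", with a Fisher's exact test for each event type. None gives a closing date.

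**Who is not seen.** Section 7.5 and footnote 13 state "Patients who have undergone prostatectomy, radiation therapy or focal prostate cancer therapy are exempt from the six-month follow-up visit requirement".

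**The concern.** Objective 1.2.12 is safety in the active surveillance population, and section 2.1 notes that most such men followed for up to 15 years will not need treatment. A lasting immune disorder that appears months after vaccination would weigh heavily in that setting. The plan asks about it, but labels the answer interval history and does not say whether it becomes an AE with grade, onset and attribution.

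Two problems follow. First, sites may classify the same late diagnosis differently, which makes a count by arm unreliable. Second, the exemption removes men because of something that happened after randomization. If the vaccine affects who leaves surveillance, the men not asked will differ between arms. The question itself needs neither an intact prostate nor a clinic visit.

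**Working it through.** The plan states no figure to reproduce here. The check is calendar arithmetic, a comparison of the collection rules, and two calculations for scale.

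**1. Length of the interval.**

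Inputs:
- Last scheduled dose: Day 140. Section 7.3 states "The Day 28, 56, 84, 112, 140 interim visits can be scheduled +/- 7 days", so Day 133-147.
- AE diary: 30 days after the last dose given (7.5, 8.4, footnote 10).
- Post-intervention visit and biopsy: "Seven to fourteen days after the last scheduled vaccine dose, participants will return for the post-intervention visit" (7.4).
- 6-month visit: 5-7 months after biopsy, or after the last dose if there was no biopsy (7.5).
- One month = 365.25/12 = 30.44 days.

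Results for a man who receives the Day 140 dose:
- Diary closes: 140 + 30 = Day 170 (163-177 over the dosing window).
- Nominal visit: 147 + 6 × 30.44 = Day 330, to 154 + 6 × 30.44 = Day 337.
- Full range: 147 + 5 × 30.44 = Day 299, to 154 + 7 × 30.44 = Day 367.
- Nominal gap: 330 − 170 = 160 to 337 − 170 = 167 days. Range: 299 − 170 = 129 to 367 − 170 = 197 days.
- Without a biopsy: visit at 140 + 182.6 = Day 323 (292-353), gap 153 days (122-183).

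Nominally the gap is about half the time from first dose to the 6-month visit (160/330 = 48%; 167/337 = 50%). For a man who stops early the diary closes sooner, for example 14 + 30 = Day 44 if his last dose was Day 14. Section 7.4 still takes AEs at the post-intervention visit if he attends it.

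**2. Which rule governs a diagnosis made on, say, Day 250?**

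| Reading | Sections | Recorded as |
|---|---|---|
| 30-day window | 7.5, 8.4, footnote 10, blank 6-month AE cell | Interval history |
| No closing date | 11.1.1, 13.5, 13.7 | AE, counted in 13.5 |

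A site could follow either reading and be within the protocol.

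**3. What a descriptive count would give.** With zero events among n men, the one-sided 95% upper bound is 1 − 0.05^(1/n).
- n = 100 (all vaccinated men assessed): 1 − 0.05^(1/100) = 2.95%.
- n = 85 (15% not assessed, an assumption): 1 − 0.05^(1/85) = 3.46%.

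The documents give no rate of definitive therapy by 6 months. At an assumed 5-15%, 0.05 × 150 = 7.5 to 0.15 × 150 = 22.5, or roughly 8-23 men, would be exempt.

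**4. What a between-arm test would give** (Fisher's exact, two-sided 5%, 100 vs 50 men; event rates are assumptions).
- With no placebo events, 9 vaccine events are needed (p = 0.030).
- 5% vs 0%: power 0.06, although the chance of at least one vaccine event is 0.994.
- 10% vs 0%: power 0.68, falling to 0.55 if 10% of men are exempt and 0.41 if 20% are.

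**The case against.** A reader might infer that late immune harm cannot enter the safety comparison and would receive no grade, attribution or serious adverse event (SAE) report. The documents do not support that.

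- Sections 11.1.1, 13.5 and 13.7 have no cut-off, and section 11 defines an AE by its timing relative to study participation, which the 6-month visit arguably is.
- The 11.2.2 SAE clock runs from knowledge of the event, with no post-dose limit. Section 11.2.3 follows related SAEs beyond 30 days.
- The blank 6-month cell is weak evidence alone: the same row is blank at the post-intervention visit, where 7.4 does collect AEs.
- Footnote 8 describes phone or email contact for safety, and that row is marked at 6 months. The exemption waives a visit, not contact.
- The interview is not limited to new disease, so worsening of a permitted condition could be reported there.

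Nor do the documents establish autoimmunity as a known effect of this vaccine. The immune-related events described in 6.2 come from the ipilimumab combination, and 6.2 labels no event without ipilimumab as autoimmune. It does report one possibly related case of thrombotic thrombocytopenic purpura.

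All of this stands, and it rules out the claim of exclusion. It does not supply the missing instruction. Section 7.4 explicitly collects AEs at the post-intervention visit; 7.5 has no equivalent for 6 months. Footnote 8 does not say that exempt men are asked about autoimmune disease or that findings go on the AE form. The low power of a test is an argument for describing the events, not for leaving their status open.

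**Conclusion.** The point holds as a gap in definition and ascertainment, not as an exclusion of late events. The 6-month autoimmune answer has no stated path to the AE data, and the sections disagree on when AE collection ends. The interval affected is nominally 160-167 days per completer (129-197 across the visit windows), taking the Day 140 dose as given on schedule.

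Exempt men are not asked the question at the visit. Their number is unknown, and a difference between arms is possible but not shown. At an assumed 15% unassessed, the zero-event bound in the vaccine arm moves only from 2.95% to 3.46%. The larger issue is therefore inconsistent recording and possible selective loss, rather than precision. A reader might go further and say that no bound can be given beyond Day 170; that assumes the 30-day reading is the only one, which it is not. The primary analysis is unaffected. The change should be made because it is cheap and serves a stated objective.

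**What to change.** - Reconcile 7.1, 7.5, 8.4, 11.1.1 and 13.7 on a single AE end date.
- State that new or worsened autoimmune disease reported through the 6-month contact goes on the AE form with grade, onset and attribution, and with SAE reporting under 11.2.2 where it applies.
- Limit the footnote 13 exemption to PSA, IPSS and DRE. Obtain the interval history from exempt men at the phone or email contact already marked for 6 months.
- In 13.5, report autoimmune events through 6 months descriptively by arm with 95% confidence intervals, and state the number of men not assessed in each arm.

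Cost: protocol and form wording, slightly more AE data entry, and one call per exempt man. No extra visit or test is needed.
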